9.4.3 Ex vivo Cytotoxicity and Synergy Analysis

All cells will be grown in RPMI-1640 medium supplemented with 10% heat-inactivated FBS and 1x antibiotics/antimycotics. Primary pre-treatment MM patient-derived CD138+ cells will be co-cultured with increasing concentrations of teriflunomide. Teriflunomide will be used because conversion of leflunomide to the active metabolite teriflunomide happens primarily in the intestine. Therefore, we consider it unlikely that conversion will occur *ex vivo/in vitro*, and that use of teriflunomide is the better option. Proliferation and cytotoxicity of primary MM cells will be measured based on quantitation of the ATP present in cells, MTS assays, and Annexin V staining; IC₅₀ values will be calculated. The cells will also be cultured with increasing amounts of teriflunomide and selected MM drugs. Examples from each class include the HDAC inhibitor panobinostat, the IMiDs lenalidomide and pomalidomide, the proteasome inhibitors ixazomib and bortezomib, the steroid hormone dexamethasone and the CD38 antibody daratumumab. To evaluate synergy, we will generate combination index (CI) values by combining teriflunomide and the FDA-approved agents at constant ratios based on the IC₅₀s, as described previously by Chou TC [45], and generate isolobograms to identify the ratios producing maximal synergy.

9.4.4 High Throughput Genomics Analysis

We will evaluate MM cells treated with teriflunomide *ex vivo* (as described in [Section 9.3.3](#)) and leflunomide *in vivo* (comparison of MM samples from baseline, after one month of treatment and at PD or CR, where applicable). DNA (from 1 million cells, *in vivo* treatment only) and RNA (from 100,000 cells, *ex vivo* and *in vivo* treatment) will be extracted according to the manufacturer's instructions for RNA isolation (Qiazol, Qiagen) and DNA isolation (DNAzol, ThermoFisher) and submitted to the COH Integrative Genomics Core for analysis. Sequencing will be performed on an Illumina Hiseq 2500. Image and data processing will be conducted using Illumina's pipeline, as well as alignment tools such as TopHat (mRNA), Novoalign (miRNA), and Bismark (DNA methylation). Custom R scripts will be used for further processing, pathway analysis, and inter-group comparisons. Genetic loci/transcripts identified by bisulfite sequencing (DNA-methylation) and RNAseq (mRNA/miRNA sequencing) will be further validated using real time RT-PCR assays.

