9.4 Ex vivo and Molecular Studies

9.4.1 Sample Collection, Transfer, and Initial Processing

Please see the Appendix for detailed procedures. Any updates to the laboratory locations or contact information will be distributed to the study team. Bone marrow specimens will be collected prior to drug administration, on day 1 of cycle 2 (all phase II patients and phase I patients enrolled at the anticipated RP2D), at progression (where applicable), and at confirmation of CR/sCR (where applicable). See [Table 10, Study Activity Calendar](#). Bone marrow aspirate (10 ml) will be collected into a sodium heparin (green-top) tube. Samples will be gently inverted 8 times to mix the sample and then promptly taken at room temperature to [name] (Kaplan CRB, RM 3016) in [name] laboratory (or her representative) for processing (so that samples can be processed within an hour of collection). [name] ([contact]) as well as the supervisors [name] ([contact]) and [name] ([contact]) will be notified in advance of sampling (at least 1 day in advance) by email. Each sample will be labeled with the participant's name, medical record number, date of collection, and actual sample collection time.

The [name] laboratory will conduct Ficoll-Paque density centrifugation and preparation of mononuclear cells (MNCs) and then transfer the sample on ice to [name] [name] at the [name] laboratory (Kaplan CRB, room 1026) for enrichment CD138-positive (CD138+) plasma cells by magnetic cell sorting, according to the manufacturer's instructions. The CD138+ MNCs will be re-suspended in complete RPMI medium, counted and stored on ice for further processing.

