11.2 Phase II/Primary Endpoint: Response

The primary endpoint is response. Response will be categorized using the IMWG response criteria for multiple myeloma [37, 38]. Table 11.2 summarizes the categories and criteria.

Table 11.2 Response Criteria

Response Category	Response Criteria
Complete response (CR)*	Negative immunofixation of serum & urine, AND Disappearance of any soft tissue plasmacytomas, AND < 5% plasma cells in bone marrow
Stringent complete response (sCR)*	CR (as defined above) PLUS: Normal FLC ratio, AND Absence of clonal cells in bone marrow by immunohistochemistry or immunofluorescence
Very good partial response (VGPR)**	Serum and urine M-component detectable by immunofixation but not on electrophoresis, OR ≥ 90% reduction in serum M-component plus urine M-component < 100mg per 24h
Partial response (PR)**	≥ 50% reduction of serum M protein and reduction in 24h urinary M protein by ≥ 90% or to < 200mg per 24h If serum and urine M protein are unmeasurable, a ≥ 50% decrease in the difference between involved and unininvolved FLC levels is required in place of the M protein response criteria If serum and urine M protein are unmeasurable, AND serum free light assay is also unmeasurable, a ≥ 50% reduction in bone marrow plasma cells is required in place of M protein, provided baseline percentage was ≥ 30%. In addition to the above criteria, if present at baseline, ≥ 50% reduction in the size of soft tissue plasmacytomas is also required
Minimal Response	• 25% but ≤ 49% reduction of serum M protein and reduction in 24-hour urine M-protein by 50 to 89% which still exceeds 200 mg per 24 hr

Response Category	Response Criteria
(MR)**, ***	
 In addition to the above criteria, if present at baseline, 25-49% reduction in the size of soft tissue plasmacytomas is also required No increase in size or number of lytic bone lesions (development of compression fracture does not exclude response)
Stable disease (SD)**	Not meeting criteria for CR, VGPR, PR, or PD

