13.5 Statistical Analysis Plan

Patient demographic and baseline characteristics, including age, gender, medical history, and prior therapy, will be summarized using descriptive statistics. For continuous variables, descriptive statistics (number [n], mean, standard deviation, standard error, median (range) will be provided. For categorical variables, patient counts and percentages will be provided.

Analysis: Observed toxicities will be summarized, for all dose levels, in terms of type (organ affected or laboratory determination), severity, time of onset, duration, serum concentration of the active leflunomide metabolite, probable association with the study treatment and reversibility or outcome.

The overall response rate and clinical benefit response rate will be calculated, for the initial and sub-analysis for all dose levels; Clopper Pearson binomial 95% confidence intervals will be calculated for these estimates. As part of the initial analysis of response, the overall response rate (patients that have confirmed sCR/CR/VGPR or PR) and clinical benefit response rate (patients that have confirmed sCR/CR/VGPR/PR/MR or SD) will be calculated among all patients included in the study even if there are

protocol treatment deviations or if the patient is later determined to be ineligible. In addition, as part of the phase II anti-myeloma activity assessment, sub-analyses will be performed where participants will be considered evaluable for response if they are confirmed eligible, receive at least 75% of leflunomide during the first cycle of therapy and have their disease re-evaluated. Response rates will also be evaluated based on number/type of prior therapy(ies) and serum concentration of the leflunomide metabolite (μ g/mL). Time to response and survival will be estimated using the product-limit method of Kaplan and Meier.

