For the studies combining teriflunomide with other agents *ex vivo*, combination Index (CI) values will be calculated using the CalcuSyn software program (Biosoft, Ferguson) to determine which of the compounds work synergistically, if any. A combination index of < 0.9 indicates synergism, whereas $CI = 0.9$ to 1.1 indicates additive effects. $CI > 1.1$ indicates antagonism. Isobogram diagrams will be generated that show the varying combination treatments and the ratio where maximal synergy is obtained.

The miRNA/mRNA expression profile and DNA methylation data will be used to identify the miRNA/mRNA and differential methylated regions (DMRs) that show significant differences between responders and non-responders after leflunomide treatment. For miRNA/RNA profiling, fold changes >3 with an FDR <0.05 will be considered significant. Assuming the dispersion of genes across replicates is 0.2 and minimum average expression is 10 reads per gene, 10 samples in each group (responder vs. non-responder) should have 89% power to detect a 3-fold difference between groups at an FDR level of 0.05.

The major goal of RNA-seq/miRNA-seq/RRBS-seq is to predict potential responders based on pre-treatment genomic profiling. A logistic regression-based algorithm with risk score formula described previously [46] will be used to build a classifier for response prediction. Differentially expressed miRNA/mRNA and DMRs together with other known clinical risk factors will be included in the

multivariable logistic regression model. The performance of the identified classifier will be evaluated with leave one out cross validation (LOOCV). Specifically, for each iteration -as part of a random selection process, one sample will be left out as the test sample; the remaining samples will be used to build a classifier, and the classifier will be used to predict the response status of the test sample. The sensitivity and specificity of the classifier will be calculated, as well as receiver operating characteristic (ROC) curve and area under the curve (AUC) to evaluate its accuracy.

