Ex Vivo and Molecular Studies Bone marrow aspirates will be promptly taken on ice to [name] in [name] lab for Ficoll-Paque density centrifugation and preparation of mononuclear cells and then forwarded to [name] [name] at the [name] laboratory for processing. The bone marrow aspirate will first be filtered through a 40 μ m mesh to avoid coagulated products. The filtrate will be carefully layered on top of Histopaque® (Sigma cat. # 1077-1) in 50 ml polypropylene centrifuge tubes. The sample will be centrifuged (with the brake set to "off") at 1500 x g for 25 minutes. The mononuclear blood cells at the interface between the Histopaque® and the top aqueous layer will be aspirated into a clean 15 ml polypropylene centrifuge tube using a glass Pasteur pipette.

The aspirated cells will then be washed twice in ice cold PBS, cells will be counted and placed on ice for enrichment of CD138-positive cells. CD138 is a transmembrane protein expressed on the surface of plasma cells. CD138-positive cells will be enriched by magnetic cell sorting according to the manufacturer's instructions (CD138 MicroBeads, Miltenyi Biotec Cat# 130-051-301). In brief, mononuclear cells obtained from the density centrifugation will be pelleted by centrifugation and incubated with CD138 magnetic beads for 15 minutes at 4 °C in MACS buffer, washed in MACS buffer and subjected to column separation. To increase the purity of the CD138-positive cells, the eluted fraction from the first column will be enriched over a second column, washed 1x in PBS, re-suspended in complete RPMI medium, counted and stored on ice for further processing. For RNA, DNA, and protein analysis of pre-treatment patient samples, 100,000 cells (RNA) and 1,000,000 cells (DNA, protein) will be pelleted and frozen at -80 °C. The remaining CD138-enriched cells will be stored in the vapor phase of a liquid nitrogen tank in freezing medium (10% DMSO, 50% FBS, 40% RPMI-1640) if the cells are not processed immediately. A small aliquot of the cell population will also be used to determine purity of the enriched cells by flow cytometry using anti-CD138-PE antibody (Miltenyi Biotec, Cat# 130-081-301). Purities of >95% will be accepted for further experiments.

All cells will be grown in RPMI-1640 medium supplemented with 10% heat-inactivated FBS and 1x antibiotics/antimycotics.

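### Profiles of CD138+ cells taken at complete response are compared with baseline as if both were myeloma cells, so drug effect is mixed with a change in cell composition

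*Combined protocol and SAP*

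**What the plan says.** Section 9.4.4 describes the in vivo profiling as a "comparison of MM samples from baseline, after one month of treatment and at PD or CR, where applicable". Section 2.6 and Table 9.3.2 also include complete-response specimens. Section 9.4.1 schedules marrow collection before treatment, on day 1 of cycle 2, at progression and at confirmation of CR or sCR. PR or VGPR alone triggers no marrow.

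Section 9.4.2 and Appendix B select cells by CD138 and require purity above 95%, measured in Appendix B with an anti-CD138 antibody. Appendix B states that "CD138 is a transmembrane protein expressed on the surface of plasma cells". No step tests clonality of the enriched cells or adjusts for the clonal share.

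In Table 11.2, sCR requires "Absence of clonal cells in bone marrow by immunohistochemistry or immunofluorescence". The marrow part of CR is "< 5% plasma cells in bone marrow". The serum and urine part of PR starts from at least a "50% reduction of serum M protein and reduction in 24h urinary M protein".

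Section 13.5 looks for "significant differences between responders and non-responders after leflunomide treatment", with more than 3-fold change and FDR below 0.05 for miRNA and RNA. It names no time point for that contrast. It gives prediction from pre-treatment profiles as the major goal of the sequencing, and it uses responder differences to search for pathways active in non-responders.

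**The concern.** A before/after comparison shows what leflunomide does to myeloma cells only if the same kind of cell is measured both times. CD138 selection does not ensure this. As the clone shrinks, normal plasma cells make up more of the enriched fraction, and at sCR no clonal cell is detectable. Genes that differ between normal and malignant plasma cells would then appear to change even if no myeloma cell had changed.

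The artefact follows depth of response, so a post-treatment comparison of responders with non-responders inherits it. A composition signal could be reported as a leflunomide signature, or could enter the pathway search that is meant to suggest complementary therapy.

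**Working it through.** **1. The plan's own power figure.** Section 13.5 gives 89% power for a 3-fold difference with 10 per group, dispersion 0.2, 10 reads per gene and FDR 0.05. An exact negative-binomial test gives 89.4% if 100 of 10,000 genes truly differ. That count is an assumption. Other counts give 85.3% (100 of 20,000) to 96.0% (1,000 of 20,000). The figure reproduces, but it takes the cell population as fixed.

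**2. Fold change from composition alone.** Let f be the clonal share of CD138+ cells and k the ratio of a gene's expression in normal to clonal plasma cells. Relative expression in the sample is f + (1 − f)k, so with no change in any myeloma cell:

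fold change = [f1 + (1 − f1)k] / [f0 + (1 − f0)k]

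Assume f0 = 0.95 and that the clone falls in proportion to M-protein, by a fraction r. Then f1 = 0.95(1 − r) / [0.95(1 − r) + 0.05]. The denominator of the fold change is 0.95 + 0.05 × 10 = 1.45 for k = 10 and 0.95 + 0.05 × 5 = 1.20 for k = 5.

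| Fall in clone | f1 | k = 5 | k = 10 | Clone-only gene (k = 0) |
|---|---|---|---|---|
| 50% (PR-like) | 0.475/0.525 = 0.905 | 1.381/1.20 = 1.15 | 1.857/1.45 = 1.28 | down 0.95/0.905 = 1.05 |
| 90% (VGPR-like) | 0.095/0.145 = 0.655 | 2.379/1.20 = 1.98 | 4.103/1.45 = 2.83 | down 0.95/0.655 = 1.45 |
| 100% (sCR) | 0 | 5/1.20 = 4.17 | 10/1.45 = 6.90 | lost |

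**3. Range.** With baseline plasma cells of 10–60% of marrow and normal plasma cells of 0.5–2% (again assumptions):

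- PR-like: clonal share 67–98%; the 10-fold gene shifts 1.1–1.4 times.
- VGPR-like: clonal share 29–92%; 1.6–3.0 times.
- CR with 1–4.9% plasma cells: clonal share anywhere from 0 to 90%.
- sCR: clonal share 0; 3.6–9.3 times.

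**4. How often the plan's rule would be met falsely.** This is a negative-binomial simulation with 10 per group, dispersion 0.2, a myeloma-cell mean of 10 reads and no difference in any myeloma cell. Non-responders are 95% clonal. The rule is fold change above 3 with p < 0.001 as a stand-in for FDR < 0.05.

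| Clonal share in responders | k = 5 | k = 10 |
|---|---|---|
| 90.5% | about 0% | about 0.01% |
| 75% | 0.7% | 10% |
| 50% | 21% | 85% |
| 0% | 93% | 100% |

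A gene equal in both cell types rejects in about 5% at nominal 0.05, as it should. Starting from 95%, a share of 75% needs 0.95(1 − r) = 0.15, an 84% fall; a share of 50% needs 0.95(1 − r) = 0.05, a 95% fall. The bottom row needs ten patients at sCR.

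**5. How many responders.** The probability of at least 10 responders of any depth among 39 patients is 0.78 at an ORR of 30% and 0.06 at 15%. CR/sCR specimens would be a subset of these.

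**The case against.** A reader might infer that no responder's post-treatment sample contains clonal cells, so that the in vivo comparison shows no drug effect at all. The documents do not support this. Only sCR requires the absence of clonal cells, and by staining that means below detection. CR requires few plasma cells, while VGPR and PR leave a reduced clone, and all four count as response.

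A reader might also take the month-1 sample as the main problem. It is the sample planned for every patient treated at the RP2D, but a PR-sized fall by then leaves about 90% of the cells clonal under the assumption above. The rule of more than 3-fold is then almost never met by composition alone. The pathway worry points the same way. Genes much lower in normal cells (k = 0.02) meet the rule in 0.04% of cases at 75% clonal and 4% at 50%.

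Other text limits the exposure. The classifier is meant to use pre-treatment profiles, and the responder contrast in Section 13.5 can be read as pre-treatment too. Appendix B item 3 names only baseline and 4 weeks for patient samples. The ex vivo and cell-line work uses no post-response cells, and taking methylation regions common across cell lines as candidates gives some protection.

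All of this stands. It does not remove the complete-response comparison from Sections 2.6 and 9.4.4 and Table 9.3.2. Section 13.5 states the 3-fold threshold for miRNA and RNA only, with none for methylation regions. It also plans gene-set enrichment, in which small coordinated shifts can count. Because the time point is unstated, features from a post-treatment contrast could still reach the classifier.

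**Conclusion.** The concern holds in a limited form. Baseline-versus-CR/sCR differences mix any drug effect with cell composition: fully at sCR, often at deep CR, possibly at VGPR, and little at PR or month 1 under the 3-fold rule. The sCR part follows from the plan's own definition and its CD138-only selection. The grading below sCR rests on assumed clonal fractions, expression ratios and a clone that tracks M-protein.

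The accurate statement is confounding, not absence of a drug effect. ORR, the ex vivo work and the cell-line work are unaffected. So is the pre-treatment classifier, unless its features come from a post-treatment contrast. The objectives concerned are exploratory, so this is a modest point, worth acting on because the remedy uses data already planned.

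**What to change.** 1. In Section 9.4.4 and Table 9.3.2, take CR/sCR specimens out of the before/after drug-effect comparison and report them separately as possibly non-clonal plasma cells. Align Section 2.6.
2. For month-1 and PD specimens, derive kappa/lambda light-chain clonality from the planned RNA-seq and report it by specimen and response group. Exclude immunoglobulin genes from the tested set. Repeat the before/after comparison adjusted for clonality as a sensitivity analysis. Note that in the responder contrast clonality may be nearly collinear with response, so adjustment there should not be the primary analysis. Restricting to specimens whose clonality stays near baseline should not be primary either, since it selects on outcome.
3. In Section 13.5, base the responder versus non-responder contrast that feeds the classifier and the pathway search on pre-treatment specimens. Label any post-treatment contrast as confounded with clonal fraction.

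Cost: revised wording, one derived variable and a little more analysis. No new samples are needed. A few late specimens leave the drug-effect comparison.

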10.0 STUDY CALENDAR

Table 10 describes required procedures. All procedures may increase in frequency if clinically indicated or oriented following toxicity. Adjustments to the treatment cycle due to a hold in study agent are detailed in [Section 5.2](#).

Table 10.0 Study Activity Calendar

	Screening ^a	Cycle 1, 2, 3		Cycle 4+ ^d	End of Treatment ^e				Active Follow-Up ^j	Long Term Follow-Up ^k
		Day 1 ^b	Day 14 ^c		Day 0 ^f	Days 1-11 ^g	Day 14 ^h	Day 30 ⁱ		
Informed Consent ^l	X ^u									
Inclusion/Exclusion Criteria ^m	X									
Registration ⁿ	X ⁿ									
Medical history ^o	X									
Physical exam	X	X		X					X	
Vital signs ^p	X	X		X					X	
Adverse events assessment ^q		X	X	X	X	X			X	
Concomitant meds review	X	X		X	X				X	
ECOG status ^r	X	X		X					X	
Pregnancy test ^s	X									
TB antigen test ^t	X									
Hepatitis A, B, C testing	X ^u									
Pulmonary function test	X ^u									
Extramedullary disease survey ^v	X ^u			X ^w	X ^w				X ^w	X ^w
Skeletal survey	X ^u									
Clinical bone marrow aspiration/biopsy with research use of leftover samples	X ^{u,y}	X ^{y,z,aa}		X ^{y,z}	X ^{y,z}				X ^{y,z}	X ^{y,z}
Research bone marrow aspiration		X ^{bb}								
CBC with differential ^{cc}	X	X	X	X					X	X
Chemistry panel ^{dd}	X	X	X	X					X	X
Myeloma labs ^{ee}	X	X ^{kk}		X	X				X	X
Response assessment ^{ff}		X ^{aa}		X	X				X	X
Research blood samples ^{gg}		X	X	X	X					
Teriflunomide clinical testing ^{hh}				X		X ⁱⁱ	X ⁱⁱ			
Leflunomide administration ^{jj}		Daily								
Cholestyramine ^g					X ^g					
Survival										X ^k

a. All screening procedures to be performed within 21 days of start of study agent except informed consent, acute hepatitis panel, skeletal survey, bone marrow biopsy, and pulmonary lung function test which may occur within 30 days of start of treatment (footnote u) and except for registration which must occur within 7 days from start of treatment (footnote n).

- b. Day 1 assessments to be performed within 5 days (120 hours) prior to Day 1 drug (except footnote u for C1 only). Day 1 safety assessments must be resulted and reviewed prior to administration of agent for the cycle that is initiating. Screening assessments, if performed within this aforementioned time frame, may serve as C1D1 assessments. Note: items with footnote "aa" are not performed for C1D1; the windows for screening assessments still apply.
- c. Day 14 evaluations have +/- 3 day window.
- d. Day 1 assessments to be performed within 5 days (120 hours) prior to Day 1 drug. Day 1 safety assessments must be resulted and reviewed prior to administration of agent for the cycle that is initiating.
- e. Reasons to end study treatment include disease progression and unacceptable toxicity. See Section 5.8 for all criteria.
- f. End of Treatment (EOT) Day 0 is defined as the day the determination to end treatment is made. EOT Day 0 assessments to be performed as soon as feasible, especially in the event of off treatment due to unacceptable toxicity and no later than 7 days after decision to end treatment; assessments performed after last dose of study agent(s) and within 7 days of the decision to end treatment may serve as EOT Day 0 assessments.
- g. EOT Day 1 is defined as the day cholestyramine administration begins; it will usually follow immediately after EOT Day 0, although it will not be deviation if this does not occur. Cholestyramine (8 grams three times daily for 11 days) will be administered according to [Section 5.7](#).
- h. EOT Day 14 assessments must occur after completion of cholestyramine, and may occur on Day 14 +/- 3 day window. If the cholestyramine administration period is extended beyond 11 consecutive days, the EOT Day 14 assessments may occur outside of this defined window.
- i. EOT Day 30 visit has a +/- 2 day window, however this window may be adjusted without deviation to ensure that it corresponds to the final teriflunomide clinical test (see footnote ee). All participants will be followed until resolution or stabilization of any serious adverse events occurring during treatment or starting within 30 days of last study drug administration or within the time to complete the EOT Day 30 assessments, which every occurs later.
- j. Active follow-up will occur for participants who have completed EOT procedures and yet to demonstrate disease progression. The active follow-up visit will take place every 28 days (+/- 5 days) from the day of the EOT Day 30 visit. Active follow-up will continue until an alternative myeloma therapy has commenced or until disease progression.
- k. Long term follow-up will occur approximately every 3 months (+/- 14 days) from the EOT Day 30 visit date for survival status. Information will be obtained by reviewing the City of Hope medical record, contacting the participant and/or a review of outside medical records. Note: this is not intended to be an all-inclusive list.
- l. Informed consent process to be fully documented: e.g. prospective participant had sufficient time for deliberation, all questions were answered, treatment options provided by MD, full study reviewed including risks, and a copy of signed consent given to participant.
- m. Inclusion/exclusion criteria are detailed in [Section 3](#).
- n. See [Section 4.3](#) for slot reservation and registration process. Treatment must begin within 7 days of registration. Documentation providing Investigator's confirmation that all eligibility criteria are met must be available prior to registration.
- o. Medical history to include review treatment history for myeloma, medical history pertaining to eligibility, and demographic information.
- p. Vital signs: Weight, heart rate, blood pressure, respiration rate, temp. Height required only at baseline.
- q. Adverse event (AE) reporting begins for events that occur after start of study agent. AE recording and reporting will continue until the completion of the EOT Day 30 visit or until resolution or stabilization of any serious AE occurring before the completion the EOT Day 30 assessments, which every occurs later.
- r. See Appendix A for ECOG performance status criteria.
- s. Serum or urine pregnancy test for women of child bearing potential only.

- t. T-Spot or other TB antigen test.
- u. Consent, acute hepatitis panel, skeletal survey, bone marrow biopsy, bone marrow aspiration, and pulmonary lung function test to be completed within 30 days prior to registration.
- v. Extramedullary disease survey required at screening for all participants with known or suspected extra-medullary disease. May include CT scan of the abdomen/pelvis, CT or x-ray of the chest, ultrasound of the liver/spleen or abdomen. Technique used at screening/baseline (if applicable) should be used throughout the study and include tumor measurements.
- w. Extramedullary disease survey required after screening/baseline only in patients with extramedullary disease present at screening/baseline. To occur every 12 weeks or upon clinical suspicion of progressive disease.
- x. Skeletal survey (including skull, all long bones, pelvis and chest) with tumor measurements (if plasmacytomas are present). To be performed at baseline/screening and when clinically indicated.
- y. Leftover bone marrow aspirate from screening/baseline, confirmation of complete response (CR/sCR, when applicable) and confirmation of progressive disease (PD, when applicable) ([Section 9.4](#)). Bone marrow aspirate will be collected into a 10mL or equivalent sodium heparin (green top) tube. Samples will be gently inverted approximately 8 times to mix the sample and then promptly taken at room temperature to [name] (Kaplan CRB, RM 3016) in [name] laboratory for processing (so that samples can be processed within an hour of collection). [name] ([contact]) as well as the supervisors [name] ([contact]) and [name] ([contact]) should be notified in advance of sampling (at least 1 day in advance) by email. Changes in laboratory contact information will not be considered protocol deviations.
- z. Perform bone marrow biopsy and/or aspirate once to confirm suspected CR, sCR, or PD.
- aa. Bone marrow and response assessments are not to be taken on Cycle 1 Day 1; screening labs will be used as baseline values.
- bb. Bone marrow aspiration for research on day 1 of cycle 2 ([Section 9.4](#)). **Note:** In the event that the research prep for the baseline bone marrow aspirate (footnote y) yields no useable product, this procedure will not be performed. In the event that this planned sample collection coincides with confirmation of suspected CR, sCR, or PD, then the clinical leftover samples (see footnotes y and z) will be used instead of a research-specific collection. See contact information for research sample transfer in footnote y.
- cc. CBC with differential: erythrocytes (RBC), hemoglobin, hematocrit, platelets, total WBC plus absolute differential counts (neutrophils, lymphocytes, monocytes, eosinophils, basophils).
- dd. Serum chemistry panel: Comprehensive metabolic panel (sodium, potassium, chloride, carbon dioxide, creatinine, urea nitrogen, calcium, glucose, albumin, total bilirubin, alkaline phosphatase, total protein, ALT/SGPT, AST/SGOT) LDH, magnesium, phosphorus, and uric acid.
- ee. Myeloma labs to include serum protein electrophoresis and immunofixation, quantitative immunoglobulins, serum free light chains and 24-hour urine studies (total protein, urine protein electrophoresis and immunofixation). Note: 24-hour urine studies to be performed at baseline for all participants, and after baseline to confirm complete response or in patients with urine-only measurable disease.
- ff. See [Section 11.1](#) for response assessment criteria.
- gg. Research blood sample collection will occur at the time of blood collection for clinical labs. Venous blood will be collected into three 4-mL purple top (EDTA) tubes, gently agitated, placed on ice and brought promptly (so that the sample can be processed within the hour) to the APCF in Shapiro room 1042. Notify the APCF ([name] or her representative) by e-mail to [contact] in advance of sampling (ideally at least a day in advance). Discarded cells from one sample will contribute to pharmacogenomic studies ([Section 9.3.1](#)). Changes in laboratory contact information will not be considered protocol deviations.
- hh. Teriflunomide clinical blood assay to be ordered as "leflunomide metabolite" miscellaneous clinical test.
- ii. Clinical testing must demonstrate teriflunomide plasma levels less than 0.02 mg/L or 0.02 µg/ml by two separate tests at least 14 days apart. If plasma levels are higher than 0.02 mg/L or 0.02 µg/ml, additional cholestyramine treatment will be considered.

jj. Participants will receive leflunomide orally on a daily basis which will be recorded on the pill diary. The first 3 loading doses will be given at a dose of 100 mg, after which treatment will continue at a dose of 20 or 10 mg daily. See administration details in [Section 5.5.1](#). **NOTE: On study visit days, participants should refrain from taking leflunomide until after blood is collected.**

kk. Myeloma labs may be repeated at C1D1 per investigators discretion and used for disease response assessment

